### **5.5 Dose Modification and Dosing Delays**

Dose modification of nivolumab is not permitted in this study. In some circumstances, it may be

necessary to temporarily interrupt study treatments as a result of AEs that may have an unclear relationship to the study drug.

Treatment must be withheld for drug-related Grade 4 hematologic toxicities, non-hematological toxicity  $\geq$  Grade 3 (including laboratory abnormalities) or selected  $\geq$  grade 2 immune-related toxicities, and severe or life-threatening AEs. Treatment can be held for up to 8 weeks from date of last treatment. If steroids are needed, participant should be treated but if treatment must be withheld for greater than 8 weeks, participant must be permanently discontinued from study treatment.

Table 2 summarizes the dose administration guidance for nivolumab that must be implemented with the indicated related AEs. Additional information related to dose changes for nivolumab for specific AEs can be found subsequently.

Participants may resume treatment with study drug when the drug-related AE(s) resolve to Grade  $\leq 1$  or baseline value, with the following exceptions:

- Participants may resume treatment in the presence of Grade 2 fatigue
- Participants who have not experienced a Grade 3 drug-related skin AE may resume treatment in the presence of Grade 2 skin toxicity
- For participants with Grade 2 AST, ALT and/or Total Bilirubin Abnormalities, dosing may resume when laboratory values return to baseline and management with corticosteroids, if needed, is complete.
- Participants with combined Grade 2 AST/ALT OR total bilirubin values meeting discontinuation parameters must have treatment permanently discontinued.
- Drug-related pulmonary toxicity, diarrhea or colitis must have resolved to baseline before treatment is resumed. Participants with persistent Grade 1 pneumonitis after completion of a steroid taper over at least 1 month may be eligible for retreatment if discussed with and approved by the Lead Study PI.

Participants with drug-related endocrinopathies adequately controlled with only physiologic hormone replacement may resume treatment after consultation with the Lead Study PI. Adrenal insufficiency requires discontinuation regardless of control with hormone replacement.

**Table 2:** Dose Modification Guidelines for Drug-Related Adverse Events

Toxicity	Grade	Hold Treatment (Y/N)	Timing of Treatment Restart	Nivolumab	Discontinue Subject

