Hematologic Toxicity	1, 2, 3	No	N/A	N/A	N/A
	4	Yes	Toxicity resolves to $\leq$ Grade 1 or baseline	Restart at same dose for the following events: Grade 4 neutropenia lasting $\leq 7$ days, Grade 4 lymphopenia or leukopenia.	Toxicity dose not resolve within 6 weeks of last infusion. Permanent discontinuation must be considered for any severe or life-threatening event.

				For all other Grade 4 Hematologic toxicities treatment with nivolumab may not be restarted.	
Non-Hematologic Toxicity Note: Exception to be treated similar to Grade 1 toxicity: - Grade 2 alopecia - Grade 2 fatigue - Grade 3 rash in the absence of desquamation, without mucosal involvement, not requiring systemic steroids, and that resolves to Grade 1 within 14 days * See section 5.5. for immune-related AE's	1	No	N/A	N/A	N/A
	2	Consider holding for persistent symptoms	Toxicity resolves to ≤ Grade 1 or baseline	Restart at same dose	Toxicity does not resolve within 6 weeks of last infusion. Permanent discontinuation must be considered for any severe or life-threatening event.
	3	Yes	Toxicity resolves to ≤ Grade 1 or baseline	Restart at same dose	Toxicity does not resolve within 6 weeks of last infusion. Permanent discontinuation must be considered for any severe or life-threatening event.
	4	Yes	Discontinue treatment	Treatment with nivolumab may not be restarted	Toxicity does not resolve within 6 weeks of last infusion. Permanent discontinuation must be considered for any severe or life-threatening event.

Note: Subjects who experience a recurrence of the same severe or life-threatening AE at the same grade or greater treatment must be discontinued from study treatment.

If treatment for a participant needs to be held in a situation that is not the result of toxicity (non-toxicity scenario), treatment can be held for up to 8 weeks. If treatment needs to be held for a period greater than 8 weeks, the participant should be permanently discontinued from study treatment.

If treatment is held, regardless if for toxicity or non-toxicity, the missed dose is considered skipped and will not be made up.

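### For most drug-related Grade 4 toxicity, the Section 5.5 text allows nivolumab to resume on recovery while Table 2 bars restart; text and table also disagree on holding for one class of Grade 3 rash

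*Combined protocol and SAP*

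**What the plan says.** Section 5.5 contains both a narrative rule and Table 2.

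- **Withholding (text).** "Treatment must be withheld for drug-related Grade 4 hematologic toxicities, non-hematological toxicity" of Grade 3 or higher, selected immune-related toxicities of Grade 2 or higher, and severe or life-threatening events.
- **Resumption (text).** "Participants may resume treatment with study drug when the drug-related AE(s) resolve to Grade" 1 or lower, or to baseline, subject to a list of exceptions. The list covers fatigue, skin toxicity, liver tests, and pulmonary toxicity, diarrhea or colitis. A following paragraph covers endocrinopathies. None mentions Grade 4.
- **Status of the table.** "Table 2 summarizes the dose administration guidance for nivolumab that must be implemented with the indicated related AEs".
- **Table 2, Grade 4 hematologic.** "Restart at same dose for the following events: Grade 4 neutropenia lasting" 7 days or less, and Grade 4 lymphopenia or leukopenia. Then: "For all other Grade 4 Hematologic toxicities treatment with nivolumab may not be restarted".
- **Table 2, Grade 4 non-hematologic.** The restart-timing cell says to discontinue, and the Nivolumab cell again says that "treatment with nivolumab may not be restarted".
- **Table 2, Discontinue Subject column.** In both Grade 4 rows the trigger is toxicity unresolved 6 weeks after the last infusion, followed by a statement that permanent discontinuation has to be considered for severe or life-threatening events. The non-hematologic Grade 2 and Grade 3 rows carry the same wording.
- **Table 2, items handled like Grade 1.** One of these is "Grade 3 rash in the absence of desquamation, without mucosal involvement, not requiring systemic steroids, and that resolves to Grade 1 within 14 days". The Grade 1 row shows no hold.

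**The concern.** Whether to re-expose a patient after a Grade 4 drug-related event is a patient-safety decision, and a protocol should answer it once. Here a site reading the narrative can find permission to resume after recovery, a site reading the Nivolumab column of Table 2 finds a bar, and a site reading the last column of the same row finds a conditional stop.

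The synopsis lists five participating centers, and safety and toxicity by CTCAE version 5.0 is a secondary endpoint. If centers resolve the conflict differently, exposure after a Grade 4 event, and any toxicity that follows it, would partly reflect which sentence was followed. The rash exception raises the same question on a smaller scale, about holding a dose rather than restarting.

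**Working it through.** The plan states no figure on this point and no arithmetic tests it. The check is to set the text and the table side by side for each class of event.

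| Drug-related event | Section 5.5 text | Table 2, timing and Nivolumab columns | Table 2, Discontinue Subject column | Result |
|---|---|---|---|---|
| Grade 4 non-hematologic | Hold; may resume on recovery | Discontinue; no restart | If unresolved at 6 weeks; otherwise to be considered | Text and table conflict; row inconsistent |
| Grade 4 hematologic, not one of the named events | Hold; may resume on recovery | No restart | As above | Text and table conflict; row inconsistent |
| Grade 4 neutropenia of 7 days or less, lymphopenia, leukopenia | Hold; may resume on recovery | Restart at same dose on recovery | As above | Agree on restart |
| Grade 3 non-hematologic, general | Hold; may resume on recovery | Hold; restart at same dose on recovery | As above | Agree on hold and restart |
| Grade 3 rash of the described class | Hold, as Grade 3 non-hematologic | Handled like Grade 1: no hold | Not applicable | Conflict on holding |

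Three steps follow from the table.

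1. *Is the silence of the text on Grade 4 meaningful?* The exception list includes a permanent bar, for combined Grade 2 liver abnormalities that meet the discontinuation parameters, and the next paragraph adds one for adrenal insufficiency. The text therefore states permanent bars where it intends them, and a reader may fairly take the absence of a Grade 4 bar at face value.

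2. *Does the table settle it?* Its guidance has to be implemented, but the same sentence calls it a summary, and no sentence ranks it above the resumption rule. For immune-related events the non-hematologic row sends the reader back to Section 5.5, where the resumption sentence stands.

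3. *Is the table consistent by itself?* In the two conflicting Grade 4 classes, restart is barred without condition. A further test of resolution by 6 weeks, and an instruction to consider permanent discontinuation, have no work to do once restart is barred. Either the last column is left over from the lower-grade rows or it is meant to soften the bar; the document does not say which.

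On the rash, the text sets its withholding threshold at Grade 3 with no rash exception. Its skin bullet lets patients resume with Grade 2 skin toxicity only if they have had no Grade 3 drug-related skin event. Neither statement refers to the class of Grade 3 rash that Table 2 exempts.

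**The case against.** The strongest reply is that the table controls. Section 5.5 makes Table 2 mandatory just before the permissive resumption sentence, and a specific prohibition can be obeyed without breaching a general permission. The last column can be read as repeated wording that adds a trigger and is simply redundant in the Grade 4 rows; it does not itself permit restart. The rash item is openly labeled an exception. Much of this stands: it makes the table the more natural guide. It does not remove the conflict, because no precedence is stated and the Grade 4 rows remain inconsistent within the table.

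Several stronger readings are tempting, and the documents do not support them.

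- *Table 2 bars restart after all Grade 4 toxicity.* It allows restart after three named hematologic events, and there the text agrees.
- *The recurrence note shows that barred patients are restarted.* The note reads: "Subjects who experience a recurrence of the same severe or life-threatening AE at the same grade or greater treatment must be discontinued from study treatment". It covers severe as well as life-threatening events, so it fits Grade 3 events and the three restartable Grade 4 events. It is compatible with the no-restart cells.
- *Sites could diverge without any deviation being recorded.* Section 11.3 counts any noncompliance with the protocol as a deviation, and restarting against Table 2 could be called one. Sub-site serious events go to the lead site within 24 hours (Section 8.5.1.4), related Grade 4 events to the DSMC within 48 hours (Section 8.5.2), and a medical monitor follows events day to day (Section 8.1).
- *Every non-exempt Grade 4 event has contradictory instructions.* The organ-specific algorithms in Section 5.7 are mostly figures not shown in the text available, and they may give clear instructions for particular events.
- *A site can never know the 14-day rash outcome when the next dose is due.* Cycles are 28 days with a window of 7 days either way. At the nominal interval, a rash starting within 28 − 14 = 14 days of an infusion has a known outcome by the next dose; at the earliest permitted dose the limit is 21 − 14 = 7 days. Later rashes may be undetermined.
- *About 70% of this population is cured by surgery.* Sections 1.2.2 and 7.1 say this of stage I and II, or early-stage, disease. For the trial population, Section 1.2.1 gives recurrence rates of about 32% (IIB) and 46% (IIC).

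**Conclusion.** The contradiction is real and limited. It covers restart after Grade 4 non-hematologic toxicity, restart after Grade 4 hematologic toxicity outside the three named events, and holding for one class of Grade 3 rash. For the two Grade 4 classes there is also an inconsistency inside Table 2.

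The documents give no rate for these events. Purely as an illustration, if 2% to 10% of the 73 planned patients had a Grade 4 event outside the exempt classes or a rash of the described class, that would be 0.02 × 73 = 1.5 to 0.10 × 73 = 7.3 patients, or about 1 to 7. The percentages are assumed and pool the two kinds of event, so the range shows scale only and is not evidence.

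The conclusion rests on the Section 5.5 text and Table 2 as they stand, and on there being no statement of precedence elsewhere in the document. It does not affect the sample-size or primary-endpoint calculation. It should be corrected because it concerns patient safety and the consistency of the safety data across sites.

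**What to change.** The sponsor should reconcile the Section 5.5 withholding and resumption text with all columns of the Table 2 Grade 4 rows and with the Grade 3 rash exception, so that each grade and toxicity class carries one instruction on holding and one on restart. The section should also state whether the text or the table governs if they differ. The clinical content is for the sponsor's medical lead to decide; no rule is proposed here.

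The cost is a wording amendment to Section 5.5 and Table 2, IRB approval of it as Section 10.2 requires, and a memo to the sites. It adds no procedures, visits or patients, and the analysis does not change.

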## Hepatic Adverse Event Management Algorithm

Rule out non-inflammatory causes. If non-inflammatory cause, treat accordingly and continue I-O therapy. Consider imaging for obstruction.

Patients on IV steroids may be switched to an equivalent dose of oral corticosteroids (e.g. prednisone) at start of tapering or earlier, once sustained clinical improvement is observed. Lower bioavailability of oral corticosteroids should be taken into account when switching to the equivalent dose of oral corticosteroids.

\*I-O therapy may be delayed rather than discontinued if AST/ALT ≤ 8 x ULN or T.bili ≤ 5 x ULN.

[figure not shown]
\*\*The recommended starting dose for grade 4 hepatitis is 2 mg/kg/day methylprednisolone IV.

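### The liver hold, stop and restart rules in Section 5.5, Table 2 and the hepatic algorithm are not reconciled, and no order of precedence is stated

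*Combined protocol and SAP*

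**What the plan says.** Four pieces of text govern what happens to nivolumab when liver tests rise.

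- **Section 5.5, resume bullet:** "For participants with Grade 2 AST, ALT and/or Total Bilirubin Abnormalities, dosing may resume when laboratory values return to baseline", with any corticosteroid management also finished.
- **Section 5.5, next bullet:** "Participants with combined Grade 2 AST/ALT OR total bilirubin values meeting discontinuation parameters must have treatment permanently discontinued".
- **Table 2 (within Section 5.5), non-hematologic rows:** Grade 3 is held and restarted at the same dose once it is back to Grade 1 or below, or to baseline. For Grade 4, treatment is discontinued and "treatment with nivolumab may not be restarted". A note in these rows reads "See section 5.5. for immune-related AE's".
- **Hepatic algorithm, Section 5.7.3, single-asterisk footnote:** "I-O therapy may be delayed rather than discontinued if AST/ALT ≤ 8 x ULN or T.bili ≤ 5 x ULN". A separate double-asterisk footnote adds: "The recommended starting dose for grade 4 hepatitis is 2 mg/kg/day methylprednisolone IV". The flowchart to which both belong is not shown.

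On the force of these texts, Section 5.5 states: "Table 2 summarizes the dose administration guidance for nivolumab that must be implemented with the indicated related AEs". Sections 5.7 and 5.7.3 describe the organ algorithms as recommendations.

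**The concern.** A site applying these rules to one patient can reach different answers depending on which sentence it reads: resume at baseline, stop for good, delay, or never restart. Liver chemistry is reviewed before each of up to 12 doses at five centers, so the rule has to be readable in the same way everywhere.

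Two things are at stake. A patient could be re-treated under one passage when another forbids it. In addition, safety and toxicity form a secondary endpoint, and the count of treatment discontinuations for toxicity would partly reflect how each site parsed the text.

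**Working it through.** The plan has no figure to reproduce here. The check sets the rules side by side, with one logical test.

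**Step 1: the two Section 5.5 bullets.** Take a patient whose AST/ALT and bilirubin have both been at Grade 2, are now back to baseline, and who has finished any steroids. The first bullet's *and/or* covers this patient, who may resume. The second bullet has at least three readings:

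- The qualifier about discontinuation parameters applies to everything. The patient stops only if the parameters are met, and the bullet does not give them.
- *Combined* means AST/ALT together with bilirubin, and such a combination is itself the trigger. The patient stops. The printed *OR* fits this reading badly.
- *Combined* joins AST and ALT, and the qualifier belongs to bilirubin alone. The patient stops if both AST and ALT reached Grade 2, or if bilirubin met the parameters.

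One patient therefore has more than one printed outcome, and the bullet has no cross-reference to settle it.

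**Step 2: order of the grades.**

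- Grade 2 liver (5.5 bullets): return to baseline required; permanent stop possible.
- Grade 3 non-hematologic (Table 2): same-dose restart at Grade 1 or below, or baseline. The row also has a 6-week limit on resolution and requires permanent discontinuation to be considered for severe events.
- Grade 4 non-hematologic (Table 2): no restart.

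Grade 2 can thus carry a stricter printed rule than Grade 3, without explanation.

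**Step 3: hepatic footnote against Table 2, Grade 4.** Let A be AST/ALT and B total bilirubin, in multiples of ULN. Delay is allowed if A ≤ 8 *or* B ≤ 5. Grade 4 means A > a or B > b. The documents name CTCAE 5.0 (Section 8.4.3) but print no values for a and b, so these are assumptions.

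- *Or*, as printed: any A > a with B ≤ 5 is both Grade 4 and eligible for delay, and so is any B > b with A ≤ 8. Overlap exists whatever a and b are.
- *And*: overlap requires a < 8 or b < 5.

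Grid check: A from 1 to 50 and B from 1 to 30 in steps of 0.5; a = 4, 8, 10, 20, 30; b = 3, 5, 8, 10, 15; 5 × 5 = 25 pairs.

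- *Or*: overlap in 25 of 25 pairs. The smallest is 810 of 4,130 Grade 4 grid points, at a = 30, b = 15.
- *And*: overlap in 9 of 25 (the five pairs with a = 4 and the other four with b = 3); none in the remaining 16.

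Grid counts are not patient frequencies; only zero versus non-zero matters. The connector decides the result in 16 of the 25 pairs. All of this is conditional on the unseen box covering Grade 4.

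**Step 4: precedence.** Table 2 is mandatory and the 5.7 algorithms are recommendations, which suggests that Table 2 governs. But its note sends immune-related events to Section 5.5, where Table 2 itself stands, while the immune-related procedures are in 5.7. No sentence ranks the passages.

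**Step 5: how many patients.** Section 5.6 gives frequency tiers. Assume each tier ends where the next begins and that the rates carry over to 73 enrolled patients:

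- Hepatitis, at least 0.1% and below 1%: 73 × 0.001 = 0.07 to 73 × 0.01 = 0.73 patients.
- Raised AST/ALT of any grade, at least 1% and below 10%: 73 × 0.01 = 0.73 to 73 × 0.10 = 7.3 patients.

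The list also places immune-mediated hepatitis and increased liver function tests in its rare tier, and gives no rate by grade, so these ranges are rough.

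**The case against.** The strongest reply is that the text is ambiguous, not contradictory. The two bullets can work as a rule and its carve-out: the first is permissive, the second mandatory for those who meet the parameters. The footnote is permissive too, and a permissive recommendation need not displace a mandatory table. The missing flowchart may define the parameters and may confine the single-asterisk footnote to a branch below Grade 4; Grade 4 hepatitis has its own mark. Few patients will be affected, and those who stop treatment remain in follow-up (Sections 5.5.1 and 7.2), so no effect on 24-month recurrence-free survival is shown.

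Much of this stands, and it rules out several stronger readings that a reader might infer:

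- *Every patient with both tests at Grade 2 must stop.* The qualifier in the second bullet prevents that conclusion.
- *A patient with normal bilirubin may be delayed at any AST/ALT value.* That follows from the footnote's words alone, but the box that limits its scope cannot be seen.
- *The footnote's limits lie above the level at which 5.5 requires a stop.* The documents give neither × ULN cut-offs for the grades nor the parameters, so the levels cannot be compared.
- *Table 2 bars every Grade 4 restart.* Its hematologic row has exceptions: "Restart at same dose for the following events: Grade 4 neutropenia lasting" up to 7 days, and lymphopenia or leukopenia.
- *The parameters are absent from the plan.* They may be in the figure. What is missing from the visible bullet is a pointer to them.

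The reply does not remove the need for a precedence rule. Suppose the Table 2 note means the bullets of Section 5.5. Those bullets name a liver grade only at Grade 2, and the general resume sentence above them sets no upper grade. Whether Table 2's Grade 4 bar applies to an immune-related liver event would then depend on a pointer that leads back to its own section.

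**Conclusion.** The point holds as a failure to reconcile. Three defects are visible without the figure: a stop bullet with several readings and an unreferenced threshold, a Grade 2 rule that can be stricter than Grade 3, and a circular pointer with no stated precedence. A fourth, the overlap between the footnote's *or* and Table 2's Grade 4 bar, does not depend on the CTCAE cut-offs but does depend on the footnote's box covering Grade 4.

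The consequence is confined to treatment exposure, patient safety and the comparability of toxicity discontinuations between sites. On the tiers in Section 5.6, at most a handful of the 73 patients would have raised AST/ALT of any grade, and the share reaching Grade 2 or above is not given. The correction is worth making because it is cheap and bears on re-treatment after liver toxicity. Which limit or outcome is clinically right is not judged here.

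**What to change.** Reconcile the two Section 5.5 bullets, Table 2 and the hepatic footnote into one consistent liver rule:

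1. Use one explicit connector, *and* or *or*, for the AST/ALT and bilirubin conditions wherever they appear together.
2. Define the discontinuation parameters beside the bullet, or cite exactly where they are.
3. Show how Grades 2, 3 and 4 relate, so that any stricter treatment of the lower grade is deliberate and explained.
4. Correct the Table 2 pointer for immune-related events.
5. State which passage governs when they differ.

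The sponsor's clinicians set the limits and outcomes. The cost is a wording amendment and a memo to sites. No tests are added, because AST, ALT and bilirubin are already drawn within 7 days before each dose.

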### 5.7.1. Procedures and Guidelines for Pneumonitis

Subjects with symptomatic pneumonitis must immediately stop receiving nivolumab and have an evaluation. The evaluation may include bronchoscopy and pulmonary function tests to rule out other causes such as infection. If the subject is determined to have study drug–associated pneumonitis, the suggested treatment plan is below.

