## Skin Adverse Event Management Algorithm

Rule out non-inflammatory causes. If non-inflammatory cause, treat accordingly and continue I-O therapy.

Patients on IV steroids may be switched to an equivalent dose of oral corticosteroids (e.g. prednisone) at start of tapering or earlier, once sustained clinical improvement is observed. Lower bioavailability of oral corticosteroids should be taken into account when switching to the equivalent dose of oral corticosteroids.

\*Refer to NCI CTCAE v4 for term-specific grading criteria.

[figure not shown]
^If SJS/TEN is suspected, withhold I-O therapy and refer patient for specialized care for assessment and treatment. If SJS or TEN is diagnosed, permanently discontinue I-O therapy.

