### 5.7.8. Procedures for Other Immune-Mediated Adverse Reactions, Including Ocular Manifestations

Nivolumab must be permanently discontinued for severe immune-mediated adverse reactions. Systemic corticosteroids treatment should be initiated at a dose of 1 to 2 mg/kg per day of prednisone or equivalent for severe immune-mediated adverse reactions.

Corticosteroid eye drops must be administered to subjects who develop uveitis, iritis, or episcleritis. Nivolumab must be permanently discontinued for immune-mediated ocular disease that is unresponsive to local immunosuppressive therapy.

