#### **8.4.3. Severity of Event**

Adverse events will be graded for severity according to the Common Terminology Criteria for Adverse Events (CTCAE) version 5.0

The following categories and definitions of intensity as determined by a physician must be used:

- Mild (Grade 1): Awareness of event but easily tolerated.
- Moderate (Grade 2): Discomfort enough to cause some interference with usual activity.
- Severe (Grade 3): Inability to carry out usual activity.
- Very Severe (Grade 4): Debilitating; significantly incapacitates subject despite symptomatic therapy.

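### Table 2's note on immune-related AEs points back to section 5.5 rather than to 5.7, so a site can miss the 5.7.8 rule that permanently stops nivolumab after a severe immune-mediated reaction

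*Combined protocol and SAP*

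**What the plan says.** Section 5.5 makes Table 2 mandatory for drug-related AEs. It then says, without a section number, that more detail on dose changes for particular AEs comes later. The note in the table's non-hematologic row says "See section 5.5. for immune-related AE's".

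The 5.5 text does contain some immune-type rules. Treatment must be withheld for, among other things, selected events at or above "grade 2 immune-related toxicities, and severe or life-threatening AEs"; the selected events are not listed there. Treatment may resume when a drug-related AE returns to Grade 1 or lower, or to baseline. Specific provisions cover fatigue, skin, liver, lung, bowel and endocrine events, and adrenal insufficiency requires discontinuation.

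For a Grade 3 non-hematologic event, Table 2 requires a hold and then permits restarting at an unchanged dose. On stopping for good it says only: "Permanent discontinuation must be considered for any severe or life-threatening event".

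Section 5.7, headed as the section for immune-related AEs, has subsections 5.7.1 to 5.7.8. The last of these, for other reactions including ocular ones, says: "Nivolumab must be permanently discontinued for severe immune-mediated adverse reactions".

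**The concern.** A cross-reference that names its own section does not take the reader to the rules that he or she needs. If the two sets of rules agreed, this would be a typing slip. They do not fully agree. On at least one question, whether the drug may be given again after a severe immune-mediated reaction, the section that the note cites is more permissive than the section that it does not cite. No sentence in the readable text says which prevails.

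The wording of the two sections makes this worse. Table 2 is described as mandatory, while 5.7 introduces its content as recommendations, so a site could reasonably treat Table 2 as controlling. Five centers have to apply these rules alike. The patients have resected disease, and the protocol says that nearly 70% of early-stage patients are cured by excision alone, so tolerance for avoidable toxicity is low.

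**Working it through.** No arithmetic applies beyond a count. The check sets the texts side by side.

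**1. The cross-reference.** Section 5.7 has eight subsections (5.7.1 to 5.7.8). The number cited by section number in 5.5 or Table 2 is 0.

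**2. Severe reactions: 5.7.8 against 5.5 and Table 2.** Section 8.4.3 supplies the meaning of the word: "Severe (Grade 3): Inability to carry out usual activity". It labels Grade 4 very severe.

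Take Grade 3 inflammation of the heart. Section 5.6 lists heart inflammation as an expected toxicity. It has no subsection in 5.7.1 to 5.7.7 (lung, bowel, liver, skin, nerve, endocrine, kidney), so it falls under 5.7.8 even if that heading is read narrowly. Suppose that it settles to Grade 1 within 6 weeks of the last infusion.

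- *Table 2, Grade 3 row:* hold, then restart at the same dose. Discontinuation has to be considered but is not required.
- *5.5 text:* the general resumption rule allows treatment again at Grade 1 or lower, and none of its exceptions covers the heart. Taking the note to remove immune-related AEs from the generic row therefore does not change the result.
- *5.7.8:* permanent discontinuation.

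These outcomes differ. The footnote to Table 2 points the same way: it requires discontinuation when the same severe event recurs, which presupposes that a first one may be followed by further dosing.

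**3. SJS/TEN: the 5.7.4 skin algorithm against 5.5 and Table 2.** The algorithm's footnote says: "If SJS or TEN is diagnosed, permanently discontinue I-O therapy". It sets no grade condition. Neither 5.5 nor Table 2 mentions SJS or TEN. Table 2 already bars restart at Grade 4, and its rash exception excludes desquamation and mucosal involvement. Below Grade 4, the general rules would on their face permit resumption. This is an omission rather than an opposing instruction.

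**4. Pneumonitis: 5.7.1 against Table 2 and 5.5.** Section 5.7.1 says: "Subjects with symptomatic pneumonitis must immediately stop receiving nivolumab and have an evaluation". The generic Table 2 Grade 2 entry says: "Consider holding for persistent symptoms". Against that row, 5.7.1 is stricter. Against the 5.5 text it is only clearer: 5.5 requires lung toxicity to return to baseline before treatment resumes, which presupposes a hold, and 5.7.1 does not say that the stop is permanent.

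**Result.** There is one real conflict (5.7.8), one omission (5.7.4) and one difference from the generic Table 2 row only (5.7.1).

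**The case against.** The strongest reply is that the note is not empty. It can be read as moving the reader from the generic row to the 5.5 text, which has lung, bowel, liver, endocrine and adrenal rules and then points onward. Section 5.7 follows shortly, under a heading that names immune-related AEs. This much stands: a reader might infer that the note leads to no immune guidance at all, and the documents do not support that. But the text it leads to lacks the 5.7.8 rule, and the onward pointer neither names 5.7 nor gives it precedence.

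A second reply is that 8.4.3 concerns AE recording, and that 5.5 uses severe differently. Section 5.5 lists severe events separately from Grade 3 non-hematologic toxicity, and the discontinue column repeats its sentence about severe events even in the Grade 2 row. This is fair, and it shows that the term is used loosely. It does not remove the conflict: for a severe event, whatever its grade, that column asks for consideration where 5.7.8 requires a permanent stop. Only if severe meant Grade 4 would the Table 2 bar on restart close the gap, and 8.4.3 gives Grade 4 a different label.

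Third, a site that reads everything and follows the stricter rule complies with all of it. That is true, but no readable sentence tells it to do so.

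Fourth, the 5.7 figures are not shown. They might list the selected toxicities or say how 5.7 relates to dosing. That limits what can be said about the whole of 5.7. It does not alter the printed note or the readable text of 5.7.8.

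Two other stronger inferences should be resisted. One is that 5.7.1 and 5.7.4 also contradict the 5.5 text; steps 3 and 4 show that they do not. The other is that 5.7 should simply override 5.5. It describes its content as recommendations, and its hepatic algorithm allows delay instead of discontinuation within stated liver limits, so a blanket override could loosen a stop rule.

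**Conclusion.** The plan is wrong as written on a minor patient-safety point that should be fixed. The self-reference is certain from the text. The substantive conflict is between 5.7.8 and the Table 2 Grade 3 row together with the general 5.5 resumption rule. It rests on taking severe as Grade 3, as 8.4.3 does, or at least as including events below Grade 4. The SJS/TEN omission and the pneumonitis contrast are secondary.

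No probability is given, because the documents do not say how often a site would work from Table 2 alone. For one patient, the consequence is re-exposure to nivolumab after a severe immune reaction that 5.7.8 says should end treatment. A reader might infer that trial results are at risk. Nothing here changes the primary endpoint, the sample size or the alpha, and there is no effect on the primary analysis.

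**What to change.** Make two wording changes.

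1. Change the Table 2 note so that, for immune-related AEs, it refers to section 5.7 and to the resumption exceptions in section 5.5.

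2. Add one sentence to 5.5, for example: *For immune-related AEs, where section 5.5, Table 2 and section 5.7 differ, the stricter hold or discontinuation rule applies. This includes the immediate stop for symptomatic pneumonitis (5.7.1), and permanent discontinuation for diagnosed SJS/TEN (5.7.4) and for severe (Grade 3 or higher) other immune-mediated reactions (5.7.8). Stricter rules in 5.5, such as discontinuation for adrenal insufficiency, remain in force.*

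Limiting the sentence to the stricter rule keeps the permissive parts of 5.7 from displacing a stop rule elsewhere. Stating the grade for 5.7.8 settles the loose use of severe. Before finalizing it, the sponsor should check the sentence against the 5.7 figures.

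The cost is amendment wording and a memo to sites. It adds no visits, tests or patients.
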